### **Sample size justification:**

Since this is a pilot study, the sample size estimation method proposed by Julious was considered in order to minimize the sample size (14). Julious proposes to employ sample size of 12 per group for a pilot study (14). Assuming the drop out rate of 20% along with the ease of blocked randomization, we propose the sample size of 16 per arm, totaling 48 patients. The estimated effect size,  $\alpha$ , and  $\beta$  corresponding to this sample size are 0.9, 0.05 (two-sided), and 0.2 respectively (15). A block size of 12 along with an allocation ratio of 1:1:1 will be employed as a randomization scheme.

**Recruitment/Treatment Periods:**

The recruitment period is planned for 24 months. The treatment period is 24 months. A biopsy will be required at Month 3, 12 and 24. Month 3 and 12 biopsies are done according to the institutional practice. No follow-up period is planned. Discontinued patients will be followed for renal function and incidence of efficacy failure at 3, 6, 12, and 24 months post-randomization. Serious adverse events will be recorded for 4 weeks after completing treatment.

## 1. Background

Every year, as the waitlist for kidney transplants grows, the number of deaths among patients wait-listed also grows. A serious shortage of this vital organ is reported to be responsible for the death of almost half of elderly patients on the waitlist (1). One approach to meet this growing demand is to expand the criteria for kidney donors to ones that have been previously unacceptable. The use of elevated KDPI and Donation after Cardiac Death (DCD) kidneys is increasing; 1,792 and 1,136 cases respectively, compared to 7,503 standard kidneys in 2008 (2). The number of available elevated KDPI kidneys rise every year; however, because of “less than ideal” (or delicate, problematic, etc) condition of these kidneys, and technical challenges it may impose, many centers do not accept these cases.

MedStar Georgetown Transplant Institute (MGTI), like many other transplant programs nationwide, maintain renal transplant patients on double- maintenance therapy of calcineurin inhibitors (CNI), and Mycophenolic acid (MPA) with steroid withdrawal, as well as antibody induction therapy. Although CNIs are one of the most common immunosuppressants prescribed, its nephrotoxicity and incidences with polyoma viral infection have been reported to be associated with less acute and subclinical rejection (12). Because of these side effects, a substantial number of clinical trials were and are being conducted to minimize and/or eliminate CNIs: However, no CNI-reduced/free standard therapy has been established so far.

One of the immunosuppressants currently being evaluated to replace CNIs in patients with CNI nephropathy is the mammalian Target of Rapamycin (mTOR) inhibitor, Sirolimus. Everolimus is a derivative of Sirolimus and belongs to this class of immunosuppressants, therefore, both drugs have similar side effect profile (4, 5). The half-life of Everolimus is almost half of Sirolimus (Everolimus 30 hours vs Sirolimus 62 hours), which makes its dose adjustment easier although it would require more frequent dosing. In clinical trials, Everolimus has demonstrated its potential role as a safe alternative in minimizing and/or eliminating CNI such as Cyclosporin A and Tacrolimus (6-9, 18).

Although the need for CNI-reduced/free therapy exists for all donor types, a growing recipient population of DCD and elevated KDPI kidneys warrants greater protection from nephrotoxicity due to their suboptimal pathology. In a pilot study conducted at University of British Columbia, CNI-free regimen using Sirolimus, MPA and steroids in high KDPI recipients demonstrated significantly better renal function with comparable graft and patient survival after a 2-year follow-up, compared to CNI, MPA and steroid therapy (10,11). So far, no study was conducted using Everolimus in DCD and/or an elevated KDPI population (clinical trials.gov).

Here, we propose to evaluate the efficacy and safety comparing Everolimus in combination with CNI-minimization regimen with standard therapy in recipients of / DCD and elevated KDPI kidneys. This study will provide pivotal information on the use of Everolimus in growing population of kidney transplant recipients.

## **Objectives:**

The primary objective of the study is to evaluate efficacy of Everolimus treatment arms compared to MMF/MPA treatment arm with respect to primary efficacy failure rate, namely, the composite efficacy endpoint, treated BPAR episodes, delayed graft function, graft loss, death or loss to follow-up, at 24 months in recipients of DCD or elevated KDPI kidneys.

## **2. Purpose and rationale**

The purpose of this pilot study is to evaluate concentration-controlled everolimus with low dose tacrolimus compared to early conversion to CNI-free regimen and MMF/MPA with standard dose tacrolimus in *de novo* renal transplant recipients of / DCD and elevated KDPI kidneys. Given tacrolimus and MMF/MPA is a widely prescribed immunosuppressive regimen in the United States, comparisons of tacrolimus and MMF/MPA regimens to investigational therapies and treatment regimens are needed. Also, considering the fact that DCD and elevated KDPI is a fast growing fraction of donors, evaluation of various regimens' effects on rather delicate DCD and elevated KDPI kidneys is necessary.

## **3. Objective**

The objective of this study is to evaluate efficacy of concentration-controlled everolimus in combination with low dose tacrolimus and early conversion to CNI-free regimen in *de novo* renal transplant recipients of DCD and elevated KDPI kidneys.

### **3.1 Primary objective**

The primary objective of this study is to evaluate concentration-controlled everolimus and low dose tacrolimus compared to MMF/MPA with standard dose tacrolimus at 24 months post-transplant with respect to the composite efficacy failure rates (treated biopsy proven acute rejection episodes (BPAR), graft loss, death, loss to follow-up) in *de novo* renal transplant recipients.

### **3.2 Secondary objectives**

The key secondary objective is to compare renal function of the everolimus treatment arms to the MMF/MPA treatment arm at 12 and 24 months post-transplantation. Renal function will be measured by the calculated glomerular filtration rate (GFR), using the MDRD (Modification of Diet in Renal Disease) formula (20).

Other secondary objectives include:

- The incidence of treated BPAR at 12 months
- The incidence of graft loss at 12 months
- The incidence of death or loss to follow up at 12 months
- Incidence of adverse events (AEs)
- Incidence of serious adverse events (SAEs)
- Incidence of new onset diabetes mellitus defined as non-diabetic patients before transplantation, who are receiving glucose lowering treatment for more than 30 days

post-transplant, or with a random plasma glucose  $\geq 200$  mg/dL (11.1 mmol/L) with 2 fasting plasma glucose values  $\geq 126$  mg/dL (7 mmol/L).

- Incidence of CMV (viremia or viruria) and BKV (viremia or viruria)
- Incidence of proteinuria by more than 3 fold or proteinuria reaching 1.5gm/day
- The comparison of the health related quality of life for patients treated with everolimus plus low dose tacrolimus to CellCept plus standard dose tacrolimus

#### **4 Study Design**

This is a 24 month, Single Center, Open-Label, Randomized, Parallel assignment, non-inferiority pilot study of safety and efficacy, comparing Everolimus with low-dose Tacrolimus (2 arms; 1 arm will involve a conversion to MMF/MPA at month 3) and the standard of care (with standard dose Tacrolimus and MMF/MPA) in recipients of DCD and elevated KDPI kidneys. For this study, either MMF 1,000 mg BID or MPA 720 mg BID will be allowed since MMF and MPA are considered to be therapeutically equivalent.

All study patients must give a signed informed consent voluntarily prior to any study-related activities. Once a signed consent is obtained, baseline assessment including laboratory testing will take place to determine patient's eligibility to participate in the study. Baseline assessments will occur in the time period starting 3 weeks pre-transplantation and ending at the time of transplantation. Eligible patients will receive Campath or Simulect as an induction therapy according to the institutional practice.

Randomization will occur within 24-hour of transplantation. Fifty patients who meet the inclusion/exclusion criteria will be randomized to receive their first dose of study drug (0.75 mg Everolimus (2 arms) or 1,000/720 mg MMF/MPA) within 24 hours of transplantation (Figure 4-1). The first dose of Tacrolimus will be given to all study participants according to our standard practice. Patients will be assigned to either continuation on low-dose Tacrolimus (Arm 1), to conversion from low-dose Tacrolimus to Mycophenolate at month 3 (Arm 2), or to standard therapy with Tacrolimus and Mycophenolate (Arm 3).

Everolimus and Tacrolimus levels will be monitored throughout the study, and respective doses will be adjusted according to the desired trough levels. Patients will be started on 0.75mg BID. Everolimus will be dosed to target trough levels of 3 to 8 ng/ml, starting on Day 7.

Earlier increase in Everolimus level may decrease Tacrolimus exposure, which may lead to under-immunosuppression; increasing the risk of acute rejection (16). Therefore, Day 7 $\pm$ 1 was chosen to initiate the first dose adjustment for Everolimus after careful consideration of the half-life of this drug and turnaround time of the trough level availability. The target Everolimus trough level was determined based on the Novartis B201 and B251 studies (17).

For Arms 1 and 2, the initial Tacrolimus dose of 0.03 mg/kg (based on ideal body weight) will be given within 24 hours of transplant. Subsequently, the target Tacrolimus trough levels will be 4 to 7 ng/ml from Day 1 to Month 3, and 2 to 5 ng/ml from Month 3 until study completion. For Arm 3, the initial dosing and adjustment will follow the institutional practice.

Patients on Arm 2 will be converted between weeks 12 and 14, after the protocol biopsy. Conversion of Tacrolimus to MMF/MPA (arm 2) will be done abruptly. On the day of conversion, MMF/MPA 1,000/720 mg will be given twice a day while no Tacrolimus will be given. In other words, there is no overlapping of Tacrolimus and MMF/MPA dosing.

For Arm 2 (after Month 3) and arm 3, MMF/MPA will be initiated at 1,000/720 mg and administered according to our standard practice in corresponding arms. Adjustment of doses may occur due to side effects, and in such cases, adjustment will follow the institutional standard practice.

All groups will be treated with corticosteroids, and prednisone will be tapered off or withdrawn according to standard practice.

[figure not shown]
For patients experiencing delayed graft function (DGF), Tacrolimus can be held up to 14 days. If this period is more than 14 consecutive days or more than two episodes of 7 days or longer, study drug discontinuation will be discussed among the study team including nephrologists. In all suspected rejection episodes, biopsy will be performed, and all patients will be treated as per our standard practice based on biopsy findings.

For patients on Arm 1 and 2 experiencing severe side effects such as complications due to delayed wound healing and mouth sores, Everolimus can be held up to 14 days. Patients who will require a prolonged discontinuation of Everolimus longer than 14 days will be withdrawn, and will be monitored as a regular follow-up until 1 month after the discontinuation. Then, patients will be monitored at a reduced follow-up schedule (Table 1).

During the 24 month study period, patients will be monitored according to the study visit schedule as listed in Table 1. The assessment to address the primary objective will be performed at month 6, 12, and 24. No interim analysis is planned. All withdrawn patients will be monitored at a reduced follow-up schedule.

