#### **Everolimus treatment arm 1:**

Therapeutic drug monitoring of everolimus and tacrolimus is mandatory throughout the study. From Day 5 on, the everolimus 0.75 mg BID dose will be increased if the trough level is < 3 ng/mL, or reduced if the trough level is > 8 ng/mL. Tacrolimus will be initiated at 0.1 mg/kg/day and adjusted according to our standard practice to achieve target trough levels. From Day 3 on, a whole blood trough concentration will be targeted for 4 to 7 ng/mL. From Month 3, the target tacrolimus trough level will be 2 ng/mL to 5 ng/mL.

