### Figure 4-1. Treatment Scheme

\*: Biopsy    tt: Target Trough level  
LD: 0.1 mg/kg/day    SOC: Standard of Care

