#### **6.5.7.2 Initiation and maintenance of Tacrolimus**

It is recommended that the initial dose of TAC be administered according to our standard of care practice within 24 hours after reperfusion of the graft. If patients experience DGF, TAC can be held for up to and including 14 days. However, TAC or study medication (ERL or MMF/MPA) must be started within 24 hours post-transplant. Subsequently, ERL dosing will be adjusted according to trough level results from the reference laboratory. Tacrolimus whole-blood trough concentrations will be determined on all study visits. Target TAC trough levels will be as follows in Table 6-1. Target therapeutic ranges for TAC C0-h levels in whole blood will be assessed at the hospital laboratory for purposes of this protocol.

If, for any time throughout the study, TAC is held for > 14 days, ERL should be discontinued and the patient discontinued from the study. These patients should be followed throughout the remainder of the study to Month 24 on a follow-up schedule. See Section 7.5, Safety assessments, Follow-up of prematurely discontinued patients.

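### The starting tacrolimus dose, its weight basis and the first day of the trough target for Arms 1 and 2 contradict each other between the synopsis and Section 4

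*Combined protocol and SAP*

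**What the plan says.** The combined protocol and SAP addresses the start of tacrolimus in Arms 1 and 2 in several places.

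- Synopsis, Everolimus treatment arm 1: "Tacrolimus will be initiated at 0.1 mg/kg/day and adjusted according to our standard practice to achieve target trough levels". It adds: "From Day 3 on, a whole blood trough concentration will be targeted for 4 to 7 ng/mL". The entry for arm 2 gives the same dose and the same day. Neither states a weight basis.
- Section 4, on Arms 1 and 2: "the initial Tacrolimus dose of 0.03 mg/kg (based on ideal body weight) will be given within 24 hours of transplant". The 4–7 ng/mL target follows from Day 1. No dosing frequency is given there.
- Section 4, a little earlier, on all arms: "The first dose of Tacrolimus will be given to all study participants according to our standard practice".
- Figure 4-1 legend: "LD: 0.1 mg/kg/day". The abbreviation LD is not expanded there or in the list of abbreviations.
- Section 6.5.5: the 4–7 ng/mL range applies from Day 1 in both everolimus arms.
- Section 6.5.7.2: "It is recommended that the initial dose of TAC be administered according to our standard of care practice". No figure is given.
- Section 6.5.4: everolimus or MMF/MPA is taken together with tacrolimus, twice a day at 12-hour intervals.

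**The concern.** The first tacrolimus order has to be written within about a day of surgery, before any trough is available to guide it. A clinician working from the synopsis and one working from Section 4 would write materially different orders for the same patient in the same arm, and would disagree on whether the Day 1 trough is subject to the target.

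The protocol itself treats early tacrolimus exposure as important. Section 4 justifies the timing of the first everolimus adjustment by the risk that reduced tacrolimus exposure leads to rejection. The Background argues that these kidneys need more protection from nephrotoxicity. The synopsis, and the objectives text that follows the Background, count delayed graft function in the primary composite, although Sections 3.1 and 10.4.1 leave it out.

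There is also an analysis consequence. The Per Protocol Set in Section 10.1 removes patients with major protocol deviations. Adherence to the starting dose cannot be judged against rules that disagree. With 16 patients per arm, mixed starting doses within an arm could blur early comparisons, and the report could not state which starting regimen was tested.

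**Working it through.** The plan has no statistical figure to reproduce here: no sample size, power or alpha value depends on the point. The check is a comparison of the texts, then a test of whether the two doses could be one dose in different units.

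**1. The texts side by side (Arms 1 and 2)**

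| Place | Starting dose | Weight basis | Start of 4–7 ng/mL target |
|---|---|---|---|
| Synopsis, arms 1 and 2 | 0.1 mg/kg/day | not stated | Day 3 |
| Section 4, arm-specific text | 0.03 mg/kg, frequency not stated | ideal body weight | Day 1 |
| Section 4, general text | standard practice, no figure | – | – |
| Figure 4-1 legend | 0.1 mg/kg/day beside LD | not stated | figure body not available |
| Section 6.5.5 | – | – | Day 1 |
| Section 6.5.7.2 | standard of care, no figure | – | refers to Table 6-1 |
| Table 6-1 | – | – | 0–3 months |

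**2. Could the two doses be the same?**

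Daily equivalent = 0.03 mg/kg × doses per day.

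- Twice daily (Section 6.5.4): 0.03 × 2 = 0.06 mg/kg/day, and 0.1 / 0.06 = 1.67.
- Per dose, the same comparison: 0.1 / 2 = 0.05 mg/kg, and 0.05 / 0.03 = 1.67.
- Three times daily, which no text specifies: 0.03 × 3 = 0.09 mg/kg/day, still not 0.1.

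Equality would need 0.1 / 0.03 = 3.33 doses a day. The figures are not one dose in different units.

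**3. In milligrams**

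The documents give no body weight, so 70 kg is an assumption, with 50–90 kg as the range. The same weight is used in both columns.

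| Weight | 0.1 mg/kg/day | 0.03 mg/kg twice daily |
|---|---|---|
| 50 kg | 5.0 mg/day | 3.0 mg/day |
| 70 kg | 7.0 mg/day | 4.2 mg/day |
| 90 kg | 9.0 mg/day | 5.4 mg/day |

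**4. Weight basis**

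If the synopsis dose is meant on actual weight, which it does not say, the ratio becomes 1.67 × (actual weight / ideal weight). It exceeds 1.67 for any patient above ideal weight. The documents give no figures from which to size this.

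**5. Start of the target**

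Day 1 and Day 3 are 2 days apart. Table 7-1 schedules tacrolimus troughs on Days 1 and 3. The Day 3 level is covered by both texts; the Day 1 level is subject to the target under Sections 4 and 6.5.5 but not under the synopsis. With 16 patients in each of two arms, that is one scheduled level in each of 2 × 16 = 32 patients.

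**The case against.** The strongest reply is that the regimen is concentration-controlled. Section 6.5.5 requires the dose to be adjusted to the trough range, and the ranges agree. Arm 1 has 4–7 ng/mL to Month 3 and then 2–5 ng/mL in the synopsis, Section 4, Section 6.5.5 and Table 6-1. Arm 2 has 4–7 ng/mL to Month 3 in the same places. (Section 4 attaches the later 2–5 range to both arms in one sentence, but its next paragraph takes Arm 2 off tacrolimus.) This stands. A reader might infer that the low-dose regimen as a whole is undefined; the documents do not support that.

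A reader might also infer that a wrong start would go uncorrected for days. Table 7-1 has a trough on Day 1, Section 6.5.7.2 calls for levels at all study visits, and two sections set the target from Day 1. Tacrolimus may also be held for up to 14 days in delayed graft function, which limits the role of the starting dose in those patients. Monitoring therefore shortens the effect of the conflict, but it does not supply the first order.

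A 3.3-fold gap is tempting (0.1 / 0.03), because Section 4 gives no frequency beside its figure. That sets a full day's dose against a single dose. Section 6.5.4 supports twice-daily dosing, so 1.67 is the like-for-like ratio.

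Finally, the standard-practice wording in Sections 4 and 6.5.7.2 can be read as general text that the arm-specific dose then refines, and LD in the figure legend is not expanded. Both are fair. They are supporting evidence only; the contradiction rests on the synopsis against Section 4.

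**Conclusion.** The point holds in a limited form. For Arms 1 and 2 the starting dose, its weight basis and the first day of the trough target are contradictory. The doses differ 1.67-fold on the protocol's own twice-daily schedule: 7.0 against 4.2 mg/day at an assumed 70 kg. Any gap between ideal and actual weight comes on top, and its size cannot be derived from the documents. The target start differs by 2 days.

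The consequences are confined to first orders, early exposure and the classification of early deviations. The trough ranges that define low-dose tacrolimus, the comparison of arms over 24 months and the sample size are not affected. It still needs correction: as written, staff using different pages would start an immunosuppressant at materially different doses. The conclusion rests on the twice-daily schedule in Section 6.5.4 applying to the Section 4 dose; no schedule of one, two or three doses a day makes the two figures equal.

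**What to change.** Reconcile the synopsis (both everolimus arms), both statements in Section 4, the Figure 4-1 legend, Section 6.5.5 and Section 6.5.7.2 so that they carry:

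- one starting rule for tacrolimus in Arms 1 and 2, with dose, frequency and weight basis;
- one start day for the 4–7 ng/mL target;
- a clear statement of whether the references to standard practice apply to Arms 1 and 2 or only to Arm 3;
- an expansion of LD in the figure legend.

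Which dose, weight basis and day are right is for the investigators to settle; this review takes no view.

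The cost is protocol wording, made through a written amendment with IRB approval under Section 12.1. No sample size or analysis method changes. For any patients already started, Section 7.3 records tacrolimus dosing on its own CRF, so the first dose actually given can be described by arm.

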## **Everolimus and MMF/MPA guidelines for dose reductions for safety reasons:**

For patients who are unable to tolerate the protocol-specified dosing schedule, dose adjustments are permitted in order to keep the patient on study drug. Reasons for study drug dose reductions may be for example, a decrease in the white blood cell count or platelet count, an increase in cholesterol or triglyceride level, gastrointestinal intolerance or other adverse events. Severe and unremitting changes may lead to study drug discontinuation. If study medication (ERL or MMF/MPA) is interrupted for safety reasons for 2 episodes of  $\geq 7$  consecutive days, or more than 21 consecutive days, discontinuation of study medication should be discussed with the sponsor.

During the course of the trial the study drugs will be administered on a BID regimen. Study medication will not be provided to patients after they have discontinued the study.

- Everolimus 1.5 mg treatment groups
  - It is recommended to reduce the dosing from the standard 0.75 mg BID to 0.5 mg BID. The dosing should, however, always follow a BID schedule.
- MMF/MPA 2,000/1,440 mg treatment group
  - MMF/MPA dose can be adjusted for gastrointestinal intolerance or a decrease in WBC. If neutropenia develops ( $ANC < 1,300/\text{mm}^3$ ) dosing with MMF/MPA should be interrupted or reduced, appropriate diagnostic tests performed and the patient managed according to local practice.

Additional information for dose adjustments based on laboratory values or other adverse events may be found in Appendix 3.

All changes in dosing of the investigational and control drug must be recorded on the Study Drug Dosage Administration Record CRF with date and reason.

The TAC dose must be adjusted to get  $C_{0-h}$  value within the pre-specified target range: for ERL Arm 1: 4 - 7 ng/mL from Day 1 until Month 3, and 2 - 5 ng/mL starting at the Month 3 Visit; for ERL Arm 2: 4 – 7 ng/mL from Day 1 until Month 3, where the patient will be converted from TAC to MMF/MPA; for SOC arm 3: 8 - 12 ng/mL starting at Day 1 until

Month 12, and 6 – 8 ng/mL from Month 12 until study completion. If TAC is held for > 14 days, study drug should be discontinued and the patient discontinued from the study.

These changes must be recorded on the Dosage Administration Record CRF.

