#### **Treatment of patients unable to tolerate oral medication**

If a patient develops a short term intolerance of oral medication after the initial dose of study medication, study drug may be temporarily interrupted (Section 6.5.5), alternatively, administration of ERL suspension may be carried out via a nasogastric (NG) tube as described below. Such administration of study drug via NG tube will be recorded on the Immunosuppressive Therapy CRF. If this period is more than 21 consecutive days or more than two episodes of 7 days or longer, study drug discontinuation will be discussed among the study team including the study nephrologists. Patients should be returned to oral medication as soon as possible after such an interruption of administration of study medication by mouth.

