### **6.5.8 Study drug discontinuation and premature patient withdrawal**

Study drug must be discontinued and the patient withdrawn from the trial if the investigator determines that continuing it would result in a significant safety risk for that patient. The following circumstances require study drug discontinuation:

- Withdrawal of informed consent
- Pregnancy
- Use of immunosuppressive drugs other than those specified by protocol except those needed to treat acute rejection.
- If the everolimus trough level is  $\leq 3\text{ng/mL}$  and cannot be maintained.
- If tacrolimus is held for more than 14 days.
- Any other protocol deviation that results in a significant risk to the patient's safety

If study drug (ERL or MMF/MPA) is interrupted for longer than 21 consecutive days or more than 2 episodes of 7 days or longer, discontinuation of study drug should be considered and discussed with the sponsor.

For patients prematurely discontinuing ERL, a post-study follow-up contact will be made at Month 3, 6, 12, 18 and 24 after transplantation, except in patients who prematurely discontinue ERL due to death, lost to follow up or patient withdrew consent. Information will be collected on serum creatinine levels, urea, rejection episodes, graft loss/ re-transplant, malignancies, opportunistic infections, patient survival and current immunosuppressive therapy.

Patients who prematurely discontinued ERL will be followed for any serious adverse event (SAE) occurring within 30 days following the last dose of ERL. These SAEs should be reported to appropriate regulatory authorities.

In addition to these requirements for study drug discontinuation, the investigator should discontinue study drug for a given patient if, on balance, he thinks that continuation would be detrimental to the patient's well-being.

A Study Drug Discontinuation form should be completed, giving the date and primary reason for stopping the study drug.

Patients may voluntarily withdraw from the study for any reason at any time. They may be considered withdrawn if they state an intention to withdraw, or fail to return for visits, or become lost to follow up for any other reason. If premature withdrawal occurs for any reason, the investigator must determine the primary reason for a patient's premature withdrawal from the study and record this information on the Study Completion CRF.

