Patients who discontinue study drug prior to the 24 month treatment period will be contacted at scheduled months 6, 12, 18 and 24 visits to obtain follow-up information and should not be considered withdrawn from the study. Information will be collected on vital signs, hospitalizations, rejection episodes, lab results (proteinuria and serum creatinine),

graft loss/re-transplant, SAEs, malignancies, opportunistic infections, patient survival, CMV infections and immunosuppressive therapy. In addition, major adverse cardiac events (MACE) will be reported during the follow-up period as a Serious Adverse Event (SAE). These include acute myocardial infarction, congestive heart failure, percutaneous coronary intervention (PCI), automatic implanted cardiac defibrillator (AICD), coronary artery bypass graft surgery (CABG), cerebral vascular accident, and peripheral vascular disease.

Biopsies will be obtained at 3, 12 and 24 months post-transplantation for all patients who agree to have this procedure done. Biopsies will be obtained at 3 months and 1-year post-transplantation biopsies are performed as a part of standard institutional protocol.

If patients refuse to return for these visits or are unable to do so, every effort should be made to contact them or a knowledgeable informant by telephone to determine the information on survival status, graft loss/re-transplant, rejection episodes, malignancies, opportunistic infections and immunosuppressive therapies. Since patients will be followed even after discontinuation of study medication, the Study Completion CRF page should only be completed at Month 24 or earlier if the patient can no longer be followed, e.g. death, lost to follow-up, withdrawal of consent.

No study drug will be provided for patients who discontinue study medication prior to study completion at 24 months.

See Section 7 for the required assessments of these patients after study drug discontinuation.

For patients who are lost to follow-up (i.e. those patients whose status is unclear because they fail to appear for study visits without stating an intention to withdraw), the investigator /the study team will show "due diligence" by documenting in the source documents steps taken to contact the patient, e.g. dates of telephone calls, registered letters, etc.

Patients who are prematurely withdrawn from the study will not be replaced by an equal number of newly enrolled patients.

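### An everolimus hold of more than 14 days means withdrawal in Section 4 but at most a discussion in 6.5.5 and 6.5.8, and no text says which rule governs

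*Combined protocol and SAP*

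**What the plan says.** Section 4 covers Arms 1 and 2 only. For severe side effects, with wound-healing complications and mouth sores as examples, "Everolimus can be held up to 14 days". Beyond that, "Patients who will require a prolonged discontinuation of Everolimus longer than 14 days will be withdrawn". The same sentence keeps these patients under regular monitoring for a month after they stop, and a reduced schedule follows.

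Section 6.5.5, in its guidelines on dose reduction for safety, covers both study drugs: "If study medication (ERL or MMF/MPA) is interrupted for safety reasons for 2 episodes of" at least seven consecutive days, "or more than 21 consecutive days, discontinuation of study medication should be discussed with the sponsor".

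Section 6.5.8 covers any interruption of everolimus or MMF/MPA, whatever the reason. Its rule applies where the drug "is interrupted for longer than 21 consecutive days or more than 2 episodes of 7 days or longer, discontinuation of study drug should be considered"; the sponsor is to be consulted. Its separate list of circumstances that require stopping study drug includes tacrolimus held for more than 14 days. It has no matching entry for everolimus.

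On patient status, 6.5.8 says that those who stop study drug before Month 24 are contacted at later visits and "should not be considered withdrawn from the study".

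Section 6.5.6, on patients who cannot take oral medication, also uses a 21-day limit: "If this period is more than 21 consecutive days or more than two episodes of 7 days or longer, study drug discontinuation will be discussed" within the study team.

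**The concern.** A hold for mouth sores or poor wound healing is an interruption for safety reasons, so the Section 4 rule and the rules in 6.5.5 and 6.5.8 reach the same patient. Section 4 orders withdrawal. The other two sections, at most, ask for a conversation. Staff who turn to 6.5.8, the section devoted to discontinuation, would not find the Section 4 rule in its mandatory list.

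This matters for the analysis because several planned outputs depend on who stopped drug and who left the study:

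- the Per Protocol Set, which Section 10.1 limits to patients who completed the study without a major violation or deviation;
- the exposure summaries in 10.3;
- the counts of discontinuation from study and from treatment in 10.5.2.

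The trial is open label, so whoever chooses between the texts knows the patient's arm. The 14-day rule also exists only for the everolimus arms, while the 21-day rule covers MMF/MPA as well.

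**Working it through.** The plan states no figure to reproduce. The check is to apply each rule to the same patient.

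**Single continuous everolimus hold for a severe side effect, Arm 1 or 2**

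| Length of hold | Section 4 | 6.5.5 | 6.5.8 |
|---|---|---|---|
| Up to 14 days | Allowed | Duration trigger not reached | Duration trigger not reached |
| 15 to 21 days | Withdrawal | Duration trigger not reached | Duration trigger not reached |
| More than 21 days | Withdrawal | Discuss with sponsor | Consider, discuss with sponsor |

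The texts agree only in the first row. From day 15 to day 21 the conflict is withdrawal against no duration trigger. After day 21 it is withdrawal against discussion. No length of hold beyond 14 days brings the sections back into agreement.

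**Exactly two holds of 7 to 14 days each**

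- Section 4: each hold is within its limit, and it has no repeat rule for everolimus.
- 6.5.5: two episodes are enough, so discussion with the sponsor is triggered.
- 6.5.8: more than two episodes are needed, so nothing is triggered.

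**Comparison across arms.** Take an interruption of 15 to 21 days. In Arm 1 or 2, an everolimus hold for a severe side effect leads to withdrawal under Section 4. In Arm 3, an MMF/MPA hold of the same length reaches no duration limit anywhere.

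**Per Protocol Set.** Take an everolimus patient who stops drug after such a hold and is followed to Month 24.

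- Under Section 4 the patient is withdrawn, and on an ordinary reading has not completed the study.
- Under 6.5.8 the patient is not withdrawn. The study completion form is filled in at Month 24, so the patient could count as a completer.

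If the patient instead restarts everolimus after 15 to 21 days, 6.5.5 and 6.5.8 have been followed but Section 4 has been breached. Section 10.1 does not say whether that would be a major deviation.

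**Full Analysis Set.** Section 10.1 defines it as all randomised patients with at least one dose, analysed by assigned arm. Membership is the same under either rule.

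**Size.** Sections 6.3 and 10.6 give 16 patients per arm. One patient is 1/16 = 6.25% of an arm, and 1/(2 × 16) = 1/32 = 3.125% of the two everolimus arms together. The documents give no expected number of holds beyond 14 days, so the number of affected patients cannot be estimated.

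**The case against.** The strongest reply is that little of this reaches the primary result, and most of that reply stands.

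- **Loss to follow-up.** A reader might infer that everolimus patients withdrawn under Section 4 would be scored as lost, and so as primary-endpoint failures. The documents do not support this. Section 4 keeps them on a reduced schedule. The synopsis, 6.5.8 and the follow-up text in 7.5 also continue contact after study drug stops. Section 10.4.3, although poorly worded, ties loss to follow-up to last contact before Month 24, not to stopping drug.
- **Withdrawn against not withdrawn.** As regards follow-up this is a clash of terms, because both texts keep the patient under observation. It is more than terminology only where an analysis set depends on completing the study.
- **Section 6.5.6.** A reader might count it as a third contradiction. It concerns inability to take oral medication, which is a different trigger, so it needs only a consistency check.
- **No rule at all.** A reader might say that the stopping rule is undefined, or that the conflict is confined to days 15 to 21. Neither is right. There are two defined rules, and they disagree for every hold beyond 14 days.
- **Other grounds for stopping.** Section 6.5.8 also requires discontinuation for a significant safety risk, or when the everolimus trough is at or below 3 ng/mL and cannot be maintained. Either could apply during a long hold. It would therefore be wrong to say that 6.5.8 calls for no action at days 15 to 21; what is true is that its duration trigger is not reached.
- **Arm asymmetry.** It arises partly because only Arms 1 and 2 receive everolimus.

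None of this removes the direct conflict between Section 4 and Sections 6.5.5 and 6.5.8.

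**Conclusion.** The point holds as an internal contradiction. For any everolimus hold longer than 14 days for a severe side effect, Section 4 and Sections 6.5.5 and 6.5.8 prescribe different consequences, with no stated precedence. The repeat-episode trigger also differs between 6.5.5 and 6.5.8.

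The choice of text affects exposure, counts of treatment and study discontinuation, and Per Protocol Set membership. Any such effect falls unevenly across arms. Each affected patient is 6.25% of an arm, and the number affected is unknown. No effect on the primary endpoint in the Full Analysis Set is shown.

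The conclusion rests on two readings: that a hold for wound-healing problems or mouth sores is an interruption for safety reasons within 6.5.5, and that a patient called withdrawn has not completed the study for the purposes of 10.1. The first affects only the conflict with 6.5.5, because 6.5.8 is not limited to safety reasons. The second affects only the Per Protocol Set consequence. The point should be fixed, but it does not by itself undermine the trial.

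**What to change.** Reconcile Sections 4, 6.5.5 and 6.5.8 so that each states the same interruption limit, the same episode count and the same consequence for everolimus. Make the mandatory list in 6.5.8 agree with the result, and check 6.5.6 for consistency. The investigators must decide which limit and consequence are clinically right; this review takes no position.

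Use one term for stopping study drug and another for leaving the study, and apply them throughout. In 10.1, say whether a patient who stops everolimus but is followed to Month 24 has completed the study, and whether exceeding the interruption limit is a major deviation.

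The cost is protocol wording, submitted as an amendment for IRB approval. Sample size, visits and data collection do not need to change.
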